This study was a prospective, nonrandomized, multicenter trial of 314 subjects implanted with a subcutaneous ICD followed for 180 days. The following adverse events were reported in the manuscript.

Table 29: Safety and Efficacy of a Totally Subcutaneous Implantable Cardioverter Defibrillator, Reported Adverse Events

Adverse Event	Patients
Infections	
Total Number	18
System Explant	4
No System Explant	14
Inappropriate Shocks	
Total Number	41
Resulting from normal device function	16
Inappropriate Sensing	25
Cardiac Oversensing	22
Non-Cardiac Oversensing	3
Death	
Total Number	8
Non-cardiac, non-sudden and unrelated to implant	5

EV ICD Pivotal Study Clinical Investigation Plan

MDT16028

Version 1.0, 02-JUL-2019

Page 155 of 165

Medtronic

Adverse Event	Patients
Unwitnessed death, device interrogation showed successful treatment of a singular ventricular arrhythmia	1
Unwitnessed death, no interrogation available, diagnosed with atypical pneumonia and hypoxia before death	1
Unknown cause of death	1

2. Maass AH, de Groot JR, van Oostrom AJ, Theuns DA, Jordaens LJ, Wilde AA, Knops RE. The entirely subcutaneous implantable cardioverter-defibrillator: initial clinical experience in a large Dutch cohort. *J Am Coll Cardiol*. 2012 Nov 6;60(19):1933-9.

This was a retrospective study using the files of 118 consecutive patients implanted with a subcutaneous ICD system. Patient experience through 18 months post-implant was included in the dataset. Adverse events observed included the following:

Table 30: The entirely subcutaneous implantable cardioverter-defibrillator: initial clinical experience in a large Dutch cohort, Reported Adverse Events

Adverse Event	Patients	Episodes
Inappropriate Shocks		
Total Number	15	33
T-wave oversensing	9	11
Myopotentials	3	4
Double Counting	1	15
Atrial Flutter	1	2
TENS Therapy	1	1
Complications		
Total Number	16	
Lead Dislodgement	3	
Device Dislodgement	1	
Infection	7	
Premature Battery Depletion	2	
Skin Erosion	2	
Explant because of need for ATP	1	

Additional Adverse Events

The above incidences of each adverse event were reported from the collection of similar Medtronic studies. Events that have been experienced in other Medtronic studies that have the potential to be experienced by subjects, or may have been reported with different terminology also include:

Anemia, Aneurysm or pseudo-aneurysm, Angina pectoris, Aphasia, Arterio-venous fistula, Asystole, Atrial septal defect, Back pain, Blood or air embolism, Bruising, Cardiac dissection, Cardiogenic shock, Cellulitis, Constrictive pericarditis, Coronary artery constriction, Coronary artery disease, Coronary artery occlusion, Coronary vein occlusion, Device capture issue, Device connection issue, Device lead issue, Device pacing issue, Device protrusion, Device signal detection issue, Diaphoresis, Dressler's syndrome, Dysplasia, Ecchymosis, Edema, Electrical conduction disorders, Electrical shock, Electromagnetic interference, Endocarditis, Erythema, Exit block, Extravasation, Failure to terminate a ventricular tachycardia/ ventricular fibrillation, Fatigue, Fever, Headache, Heart block, Heart rate increase, Hematuria, Hyperkalemia, Hypertension, Impedance decreased, Impedance increased, Implant site abscess, Implant site complication, Implant site discomfort, Implant site drainage, Implant site seroma, Implant site swelling, Inappropriate device detection, Inappropriate device programming, Inflammation, Insomnia, Lead insertion tool delivery problem, Local swelling, Loss of consciousness, Mental status change, Musculoskeletal discomfort, Myocardial damage, Myocardial irritability, Neck pain, Necrosis, Neurological symptoms, Numbness at incision site, Numbness in hand, Panic attack, Paresthesia, Pericardial rub, Phlebitis, Poor hemodynamic recovery, Presyncope, Reduced cardiac output, Reduced perfusion, Respiratory failure, Restlessness, Retrosternal pain, Scar or scarring, Sepsis, Septic shock, Skin injuries, Skin reaction, Sleep apnea, Stroke, Subcutaneous emphysema, Sudden cardiac death, Thoracic pain, Thrombocytopenia, Thromboembolism, Thrombosis, Nerve damage, Transient ischemic attack, Urticaria, Valve damage, Vascular trauma, Vasovagal reaction, Venous insufficiency, Venous stenosis, Ventricular extrasystole, Vessel perforation or laceration, Vessel spasm, Vomiting, Weakness.

Appendix F: Participating Investigators and Institutions

A complete list of participating investigators and institutions will be provided under separate cover.

Appendix G: Ethics Committee and Competent Authority List

A complete list of participating Regulatory Bodies, Competent Authorities, and Ethics Committees and their Chairperson(s) that will be utilized as part of the study will be distributed under separate cover, upon request.

Appendix H: Previous Clinical Investigations

A complete bibliography and summary of relevant literature, summary and results of preclinical testing, and summary of results of previous clinical investigations is provided in the Investigator's Brochure.

Appendix I: Chronic Defibrillation Testing Protocol

Each subject will be induced to produce up to two episodes of SSVA and allowed two shock attempts to convert each SSVA from the EV ICD, for up to a total of 4 potential shocks from the EV ICD (see Figure 11). Starting therapy polarity is at the discretion of the physician (in the programmed setting).

[figure not shown]

Figure 11: Diagram outlining the process of chronic SSVA induction and defibrillation testing

Episode 1

Program Rx1 and Rx2 therapies as follows:

	Rx1	Rx2
NID	30/40	NA
Redetect NID	NA	9/12
VF Therapy Status	ON	ON
Energy	30J	40J
Pathway	As programmed	As programmed

If Episode 1, Rx1 or Rx2 is successful in terminating the episode, the EV ICD System will have passed chronic defibrillation testing criteria. No additional inductions are required, and it is recommended to leave the system implanted with no changes.

EV ICD Pivotal Study Clinical Investigation Plan

MDT16028

Version 1.0, 02-JUL-2019

Page 161 of 165

Medtronic

Episode 2

	Rx1	Rx2
NID	9/12	NA
Redetect NID	NA	9/12
VF Therapy Status	ON	ON
Energy	40J	40J
Pathway	Opposite of programmed	Opposite of programmed

If Episode 2, Rx1 or Rx2 is successful in terminating the episode, the EV ICD System will have passed chronic defibrillation testing criteria. No additional inductions are required, and it is recommended to leave the system implanted with no changes.

If both Rx1 and Rx2 fail in Episode 2, the EV ICD System will have failed chronic defibrillation testing criteria and the next steps are at the physician's discretion. Medtronic recommends EV ICD device or lead revision (at a minimum), or system removal.

Prior to inducing and throughout the chronic defibrillation protocol, it is recommended to consider the following to improve defibrillation outcome or troubleshooting in the event of failure of first episode(s):

- Check for/resolve high impedance values
- Check for/resolve air in tunnel (e.g., fluoroscopy)
- Check for/resolve gastric bubbles (gas)
- Press on device pocket during testing
- Perform defibrillation during held end tidal expiration (end expiration apnea)

Appendix J: Applicability to CMS Beneficiaries

There is a high prevalence of ventricular tachycardia treatable by ICD therapy in the Medicare population. Medicare claims data from 2017 (the most recent currently available) shows 52,967 ICD insertion procedures (with transvenous leads) and an additional 1,657 procedures for subcutaneous ICD insertions.^{xxx} As described in the background section of this CIP, subcutaneous ICD systems are currently the only available non-transvenous ICD systems. We anticipate that the EV ICD system will provide alternative option for provider consideration in cases where non-transvenous ICD systems are necessary to provide access to potentially life-saving ICD therapy in patients where vascular access is challenging or compromised.

The EV ICD trial is designed to ensure applicability of the results to the Medicare population. Of the up to 60 sites worldwide, approximately 20 will be in the US. In addition, while the EV ICD study will be open to patients aged 18 and older, the trial will aim to enroll approximately 30% of patients in the US 65 years of age or older.

^{xxx} Medicare Physician/Supplier Procedure Summary data. Available at: <https://www.cms.gov/Research-Statistics-Data-and-Systems/Statistics-Trends-and-Reports/Physician-Supplier-Procedure-Summary/index.html>

EV ICD Pivotal Study Clinical Investigation Plan

MDT16028

Version 1.0, 02-JUL-2019

Page 163 of 165

Medtronic

EV ICD Pivotal Study Clinical Investigation Plan

MDT16028

Version 1.0, 02-JUL-2019

Page 165 of 165

Medtronic

17. Version History

Version	Summary of Changes	Author(s)/Title
1.0	Initial version.	[name], Sr. Clinical Research Specialist

7.6 Demographic and Other Baseline Characteristics	16
7.7 Treatment Characteristics	16
7.8 Interim Analyses	16
7.9 Evaluation of Objectives	17
7.9.1 Primary Objective #1: Safety	17
7.9.2 Primary Objective #2: Efficacy	20
7.9.3 Ancillary Objective #1: Appropriate and Inappropriate Shocks	25
7.9.4 Ancillary Objective #2: Electrical Performance	25
7.9.5 Ancillary Objective #3: Extracardiac Pacing Sensation	26
7.9.6 Ancillary Objective #4: Asystole Pacing	27

7.9.7	Ancillary Objective #5: ATP Performance	28
7.9.8	Ancillary Objective #6: Adverse Events.....	28
7.9.9	Ancillary Objective #7: Chronic Defibrillation Testing	29
7.9.10	Supplemental Analysis	30
7.10	Safety Evaluation	31
7.11	Managing COVID-19 Impact	31
7.12	Changes to Planned Analysis	32
8.	Validation Requirements.....	32
9.	Appendix	33
9.1	Analysis for Market Approval Outside the US.....	33

1. Version History

Version	Summary of Changes	Author(s)/Title
1.0	
 Not Applicable, New Document 	[name], Prin Statistician
2.0	
 Cover page, Clinicaltrials.gov identifier is added Section 6.2, PASS output of sample size calculation for primary efficacy endpoint is added Section 7, 7.1.1, 7.4, 7.9.8.4 and 7.10 are updated per ISO 14155:2020 requirements Section 7.1.3, analysis sets for primary and sensitivity analyses are clarified Section 7.5, hierarchical testing order is removed Section 7.8, timepoints of DMC meetings are added and the availability of DMC closed report is clarified Section 7.9.1.4, confirmatory and sensitivity analyses for primary safety objective are documented Section 7.9.2.4, details of confirmatory and sensitivity analyses for primary efficacy objective are provided Section 7.9.2.5, subjects who complete the defibrillation protocol are defined Section 7.9.6.4, programming parameter for asystole pacing is clarified Section 7.9.9.2, clarification on the endpoint analysis for chronic defibrillation testing is added Section 7.9.9.5, analysis for chronic defibrillation testing per physician discretion is replaced with original CIP language Section 7.9.10, supplemental analysis of post shock pacing effectiveness is added Section 7.11, how to manage COVID-19 impact is added Section 7.12, changes to planned analysis are updated 	[name], Prin Statistician

Version	Summary of Changes	Author(s)/Title
	
 Analysis of market approval outside the US is moved to section 9.1 in the appendix which is new, and details of the analysis are clarified 	

2. List of Abbreviations and Definitions of Terms

Abbreviation	Definition
AE	Adverse Event
ANZ	Australia and New Zealand
ATP	Antitachycardia pacing
CEC	Clinical Events Committee
CIP	Clinical Investigation Plan
DMC	Data Monitoring Committee
EMEA	Europe, Middle East, and Africa
EV ICD	ExtraVascular Implantable Cardioverter Defibrillator
GEE	Generalized Estimating Equations
ICD	Implantable Cardioverter Defibrillator
OPC	Objective Performance Criterion
PHD	Pre-hospital Discharge Visit
PMA	Pre-Market Application
SAP	Statistical Analysis Plan
S-ICD	Subcutaneous Implantable Cardioverter Defibrillator
SSVA	Sustained shockable ventricular arrhythmia

3. Introduction

This Statistical Analysis Plan (SAP) has been designed to document, before data are analyzed, the rationale for the study design, and the planned analyses that will be included in study reports. This SAP does not limit the analysis in reports. Additional analysis of the study data beyond this plan may be needed. This SAP is developed for the EV ICD Pivotal study, based on the Clinical Investigation Plan (CIP) version 1 dated July 02, 2019.

Today, implantable cardioverter defibrillator (ICD) therapy is the treatment of choice for subjects who are at risk for sudden cardiac death due to life-threatening ventricular arrhythmias. Traditional ICD systems with transvenous leads are considered standard of care for primary or secondary prevention of

tachyarrhythmic death. However, these systems have limitations. Short- and long-term complications arising from ICD systems with transvenous leads, such as infection, pneumothorax, venous thrombosis, lead dislodgement, lead malfunction, and lead perforation, have persisted for decades as impediments to ICD usage. As a result, there is demand for novel ICD systems that circumvent the potential disadvantages of transvenous ICD systems by preserving the heart and vasculature.

Medtronic has developed an extravascular ICD system which uses a substernal lead rather than a transvenous or a subcutaneous lead. The EV ICD System has similar capabilities to a single-chamber transvenous system while avoiding leads in the heart or vasculature. Compared to current market-released non-transvenous subcutaneous ICDs, the EV ICD System includes a smaller device that uses less defibrillation energy which may result in longer battery life and has the additional capabilities to deliver pacing therapies such as antitachycardia pacing (ATP) and backup asystole pacing from a single device.

In order to develop and evaluate a newly designed system for the substernal space, Medtronic completed pre-clinical research evaluations of substernal defibrillation, pacing, and sensing, and subsequently initiated three acute human clinical research feasibility studies to explore the potential development of a future chronic implantable extravascular defibrillation system with a lead implanted in the substernal space. Later, a first-in-human chronic pilot study was initiated based on the assurance from acute feasibility data. The acute feasibility and pilot studies contributed to the advancement of the EV ICD program, including refinement of the device, algorithm and implant procedure.

The EV ICD Pivotal study aims to demonstrate the safety and efficacy of the EV ICD System: a complete single-chamber extravascular ICD system with the lead implanted subinternally.

4. Study Objectives

4.1 Primary Objectives

The first primary objective is to demonstrate the freedom from major complications related to the EV ICD System and/or procedure at 6 months post-implant exceeds 79% Objective Performance Criterion (OPC). The endpoint is defined as a subject's first occurrence of a major complication related to the EV ICD System and/or procedure, as determined by an independent Clinical Events Committee (CEC), that occurs on or prior to 6 months (182 days) post-implant.

For an adverse event to meet the endpoint, the event must have occurred within 182 days (inclusive) of the EV ICD System implant and be adjudicated by the CEC as being a major complication related (causal relationship) to the EV ICD System and/or procedure. Major complications are those complications resulting in:

- Death

- Permanent loss of defibrillation function (specifically shock) due to mechanical or electrical dysfunction of the device
- Hospitalization
- Prolongation of an existing hospitalization by at least 48 hours
- System revision (reposition, replacement, explant)

The second primary objective is to demonstrate the defibrillation efficacy at implant of the EV ICD System exceeds 88% (OPC). The endpoint, defibrillation testing success, is defined as:

- Single sustained shockable ventricular arrhythmia (SSVA) conversion at 20J, or
- Conversion of two consecutive episodes of SSVA at 30J in final system configuration.

Notes:

- In one of the two consecutive SSVA episodes, up to two 30J shocks are permitted.
- To achieve final system configuration, changing the position of the ICD generator and/or the lead, or changing shock polarity is permitted.
- Subjects can return for testing on another day if testing is not fully completed on the day of implant.
- If SSVA cannot be induced, the EV ICD System must be removed (refer to CIP section 8.5.8).
- For more information on the rationale behind these objectives, refer to section 7.9 (i.e., CIP section 12).

4.2 Ancillary Objectives

- Characterize appropriate and inappropriate shocks
- Characterize electrical performance (pacing capture thresholds, pacing impedance, sensing amplitudes) over time
- Characterize extracardiac pacing sensation
- Characterize asystole pacing
- Summarize ATP performance with spontaneous arrhythmias
- Summarize adverse events
- Characterize the EV ICD defibrillation testing success rate at 6 months post-implant.

5. Investigation Plan

The EV ICD Pivotal Study is a prospective, multi-center, single-arm, non-randomized, pre-market clinical study. Enrollment will include up to 400 subjects at up to 60 sites worldwide. Subject inclusion/exclusion criteria can be found in CIP section 7.

Participating geographies are expected to include but are not limited to: ANZ (Australia and New Zealand), Canada, EMEA (Europe, Middle East, and Africa), Hong Kong, Japan, and the United States.

[figure not shown]
Participating sites that enroll faster than others will be allowed to do so to maintain an adequate enrollment rate. However, to ensure a reasonable distribution of experience and minimize site bias in

study results, the maximum number of subjects enrolled at each site will be capped at 35 (approximately 10% of total enrollments).

The expected study duration is approximately 3 years from the study's first enrollment. The enrollment period is expected to take approximately 15 months. Individual subjects may be participating in the study for a period of minimum 2 to approximately 3.5 years. The duration of individual subject participation will vary based on timing of site activation, timing of enrollment and enrollment rate. Subjects will undergo assessments at Baseline, Pre-Hospital Discharge, 2 Weeks, 3 Months, 6 Months, and every 6 months thereafter until official study closure. Official study closure is defined as when Medtronic and/or applicable regulatory authority agency or governing body requirements have been satisfied per the CIP and/or by a decision by Medtronic or regulatory authority to stop or close the study.

The following diagram provides an overview of the EV ICD Pivotal Study. This can also be found in CIP section 5.

Figure 1: Overview of the EV ICD Pivotal Study

6. Determination of Sample Size

As stated in the CIP, there are two primary objectives (safety and efficacy), and each objective requires 292 subjects to, in the case of the safety objective, undergo an implant attempt of the EV ICD System,

[figure not shown]
and in the case of the efficacy objective, complete the pre-specified defibrillation testing protocol (see CIP section 8.5.7 for details). Since the defibrillation protocol may not be initiated until an implant attempt occurs, the overall sample size requirement will be derived from the efficacy objective; at least 292 subjects will undergo the defibrillation testing protocol, which may result in more than 292 subjects undergoing an implant attempt to satisfy this requirement. To further account for subjects who enroll in the study but exit prior to an implant attempt (19% of 26 enrolled subjects in the EV ICD Pilot study did not undergo an implant attempt), up to 400 subjects may be enrolled.

6.1 Primary Objective #1: Safety

An Objective Performance Criterion (OPC) of 79% was chosen based on prior precedent to evaluate the primary safety objective metric of the EV ICD System/procedure-related major complication-free rate at 6 months. The estimated EV ICD System/procedure-related major complication-free rates through 6 months are provided in Figure 2 (i.e., CIP Figure 9). They are modeled using a Weibull distribution assuming a rate of 90% at one month and 86% at 6 months. A solid line denoting the Objective Performance criterion of 79% is also provided. It is also assumed that attrition (exit or death) will follow a Weibull distribution, with an attrition rate of 9% at one month (allowing for unsuccessful implants) and 16% through one-year post-implant.

The trial was simulated 10,000 times. Each time a sample size of 292 subjects had a time to safety endpoint simulated and a time to attrition simulated using the assumptions above. Using these data, a lower confidence bound for the 6-month Kaplan-Meier freedom from safety endpoint rate was generated using the log scale for each simulation of the trial. It was determined that based on these assumptions and the requirements of a false positive rate (α) controlled at 2.5%, a sample size of 292 subjects undergoing an implant attempt is required to allow for 90% power of assessing this objective.

[figure not shown]
Figure 2: Estimated Freedom from System/Procedure-related Major Complications

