12.3.1. Primary Objective #1: Safety

An Objective Performance Criterion (OPC) of 79% was chosen based on prior precedent to evaluate the primary safety objective metric of the EV ICD System/procedure-related major complication-free rate at 6 months. The estimated EV ICD System/procedure-related major complication-free rates through 6 months are provided in Figure 9. They are modeled using a Weibull distribution assuming a rate of 90% at one month and 86% at 6 months. A solid line denoting the Objective Performance criterion of 79% is also provided. It is also assumed that attrition (exit or death) will follow a Weibull distribution, with an attrition rate of 9% at one month (allowing for unsuccessful implants) and 16% through one-year post-implant.

The trial was simulated 10,000 times. Each time a sample size of 292 subjects had a time to safety endpoint simulated and a time to attrition simulated using the assumptions above. Using these data, a lower confidence bound for the 6-month Kaplan-Meier freedom from safety endpoint rate was generated using the log scale for each simulation of the trial. It was determined that based on these assumptions and the requirements of a false positive rate (alpha) controlled at 2.5%, a sample size of 292 subjects undergoing an implant attempt is required to allow for 90% power of assessing this objective.

Figure 9: Estimated Freedom from System/Procedure-related Major Complications

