7.5 Adjustments for Multiple Comparisons

There is no adjustment for multiple comparisons. However, both the primary safety and efficacy objectives will be evaluated at a one-sided significance level of 0.025. Because a subject may be included in the analysis for the primary safety objective but not the efficacy objective if the subject does not complete the defibrillation protocol, the primary safety and efficacy objectives are not independent.

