7.9.1.4 Analysis Methods

Results will be summarized in aggregate using descriptive statistics. The total number of major complications experienced by subjects for whom an implant is attempted will be summarized. The primary analysis for primary safety endpoint will be based on the endpoint definition described in section 7.9.1.2. Subjects not experiencing an event will be censored at their last point of contact. The 182-day freedom from major complication rate will be generated using the Kaplan-Meier method, along with a two-sided 95% confidence band based on a log-log transformation. If the lower bound is at least 0.79 (79%), the objective will be considered met.

If any adverse events that occurred within 182 days (inclusive) of the EV ICD System implant attempt were adjudicated by the CEC as being major complications and the relatedness to the EV ICD System and/or procedure was determined by the CEC as “probable”, a sensitivity analysis will be conducted with such adverse events included as having met the primary safety endpoint. An additional sensitivity analysis may be performed including major complications with a system or procedure-relatedness classification of “possible”, should there be any such major complications.

Comparison against the pre-specified OPC with the full cohort of subjects that have undergone an implant attempt is considered a confirmatory analysis of this objective.

Noninformative censoring is assumed in the primary analysis. In the situation where the attrition rate is higher than expected or there appears to be a systematic reason for attrition that may bias the results, the assumption of noninformative censoring may no longer hold and a sensitivity analysis such as a tipping point analysis may be considered.

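### The 90% power claimed for the safety objective belongs to a log-scale Kaplan-Meier bound; the log-log bound that decides the objective gives about 84% at 292 implant attempts

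*SAP*

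**What the plan says.** **Sizing.** SAP 6.1 and CIP 12.3.1 describe the same simulation of 10,000 trials. "Each time a sample size of 292 subjects had a time to safety endpoint simulated and a time to attrition simulated using the assumptions above". The event-free curve is "modeled using a Weibull distribution assuming a rate of 90% at one month and 86% at 6 months". Attrition is also Weibull, "with an attrition rate of 9% at one month (allowing for unsuccessful implants) and 16% through one-year post-implant". In each simulated trial the lower bound for the 6-month "Kaplan-Meier freedom from safety endpoint rate was generated using the log scale for each simulation of the trial". With the false positive rate required to be held at 2.5%, the conclusion is that "a sample size of 292 subjects undergoing an implant attempt is required to allow for 90% power of assessing this objective".

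**Analysis.** SAP 7.9.1.4 estimates the 182-day freedom rate by Kaplan-Meier, "along with a two-sided 95% confidence band based on a log-log transformation". The rule is: "If the lower bound is at least 0.79 (79%), the objective will be considered met". The same section calls this comparison in the full implant-attempt cohort confirmatory. SAP 7.5 states that "both the primary safety and efficacy objectives will be evaluated at a one-sided significance level of 0.025".

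**Nothing links the two.** CIP 12.4.4 asks for a two-sided 95% bound and names no transformation. SAP 7.12, which lists changes to the planned analysis, does not mention the transformation. Neither document gives a power for the log-log bound.

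**The concern.** The sizing and the decision use different lower bounds. At event-free rates of 80% to 90% the log-log bound lies below the log-scale bound for the same data, so it is harder to clear 0.79 with it. A power simulated with the log-scale bound therefore overstates the power of the planned test.

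Two things are at stake. First, the stated chance of missing a primary objective under the planning assumptions is wrong. Second, SAP 7.8 has the DMC see conditional power for this objective and allows it to consider futility. If that calculation borrowed the log-scale bound from SAP 6.1, it too would be optimistic.

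**Working it through.** **Inputs**

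- 292 implant attempts; S(1 month) = 0.90 and S(6 months) = 0.86; attrition 9% at 1 month and 16% at 12 months (SAP 6.1).
- Success if the lower bound at day 182 is at least 0.79 (SAP 7.9.1.4).
- One-sided 0.025, z = 1.96 (SAP 7.5).

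**Weibull shapes**

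- Events: ln[ln 0.86 / ln 0.90] / ln 6 = ln(1.4315)/1.7918 = 0.200.
- Attrition: ln[ln 0.84 / ln 0.91] / ln 12 = ln(1.8487)/2.4849 = 0.247.
- Using 30, 182 and 365 days instead gives 0.199 and 0.246, and 13.7% attrition by day 182.

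**Bounds**, with S the Kaplan-Meier estimate and v the Greenwood sum (the variance of ln S):

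- Log: S × exp(−1.96√v)
- Log-log: S raised to the power exp(1.96√v / |ln S|)

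**Effect on one data set.** Take 292 subjects, no censoring and 49 events: S = 243/292 = 0.8322 and √v = √[(1 − S)/(292 S)] = 0.0263.

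- Log: 0.8322 × exp(−1.96 × 0.0263) = 0.790, which passes.
- Log-log: 0.8322^exp(0.0515/0.1837) = 0.784, which fails.

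The log-log bound first passes at 47 events (S = 245/292 = 0.839, bound 0.792). Without censoring, the planned rule thus tolerates two fewer events than the simulated one.

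**Full simulation at n = 292.** Event and attrition times were independent Weibull variables. Ranges are over separate runs of 20,000 to 100,000 trials.

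| Bound | Power | Type I error at a true rate of 79% |
|---|---|---|
| Log (SAP 6.1) | 89.3% to 89.8% | 3.6% to 3.9% |
| Log-log (SAP 7.9.1.4) | 83.5% to 84.0% | 1.9% to 2.2% |

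The stated 90% is reproduced with the log-scale bound. The gap to log-log cannot be simulation noise: with 10,000 trials the standard error at 90% is √(0.9 × 0.1/10,000) = 0.003, so 6 points is about 20 standard errors.

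**Could "log scale" be loose wording for log-log?** No. Log-log falls about 6 points short, and still gives only 86.7% if attrition is removed altogether. It reaches 91.3% only at one-sided 5%, which is not the stated level.

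**Log-log power at larger numbers of attempts**

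| Attempts | Basis | Power |
|---|---|---|
| 307 | 292 completers if 20 of 21 complete testing, as in the pilot (CIP 3.1): 292 × 21/20 | 85.4% to 86% |
| 324 | 400 enrolled less 19% exiting before an attempt: 400 × 0.81 | 87.4% to 88% |
| 350 | search for 90% | 89.4% to 90.1% |

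**The case against.** The strongest reply is that only a planning statement is wrong. The decision rule is fully specified, and its log-log bound keeps the type I error below 2.5%. The discrepancy raises the sponsor's risk of missing the objective; it does not raise the risk of passing an unsafe device. All of that stands, and it is why the test itself should not change.

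A second reply is that 292 attempts is a floor. SAP 6 and CIP 12.3 derive the sample size from the efficacy objective and expect that attempts may exceed 292. This also stands, and it narrows the shortfall to about 2 to 5 points at 324 to 307 attempts. It does not remove it. Both documents tie the 90% to 292 attempts. The 324 figure needs the enrolment maximum of 400 to be reached and rests on a 19% exit rate from 26 pilot subjects. Even then power stays below 90%.

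A third reply is that the log-scale type I error is beside the point, because no planned analysis uses that bound. That is fair as to the trial's error control. It still matters for the remedy: at 292 attempts no single one of the two bounds has both properties claimed in SAP 6.1, since the one giving 90% power exceeds 2.5% and the one holding 2.5% gives about 84%.

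**Conclusion.** The point holds. The 90% in SAP 6.1 and CIP 12.3.1 is correct for the method described beside it, but that is not the method that decides the objective. For the planned log-log bound, power at 292 attempts is about 84%, so the chance of missing the objective when the planning assumptions are true is about 16% instead of 10%. Power is about 86% at 307 attempts and about 88% at 324, and reaches 90% at about 350.

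These figures assume the plan's Weibull curves, censoring independent of events, Greenwood variance and a pointwise bound at day 182. SAP 7.9.1.4 speaks of a band; a simultaneous band would give lower power still. The validity of the primary analysis is not in question.

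**What to change.** 1. Keep the log-log interval in SAP 7.9.1.4. Do not bring the analysis back to the log scale, because that bound does not hold 2.5%.
2. In SAP 6.1, re-run the existing simulation with the log-log lower bound and replace the 90% claim. Suggested content: 292 implant attempts give about 84% power; about 88% would be reached at 324 attempts, assuming 400 enrolled and 19% exiting before an attempt. State that the overall sample size remains driven by the efficacy objective.
3. Record the correction in SAP 7.12, and state in SAP 7.8 that conditional power for the DMC uses the log-log rule.
4. Align CIP 12.3.1 at its next revision. An amendment needs the approvals listed in CIP 14.6, so the SAP correction should not wait for it.

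The cost is SAP wording and one simulation re-run. The stated power becomes less favourable. No patients are added, and the endpoint, analysis set and decision rule are unchanged.
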